### Revision Chronology

GlaxoSmithKline Document Number	Date	Version
2016N275350_00	2016-SEP-12	Original
2016N275350_01	2016-DEC-13	Amendment No. 1

1. Psoriasis Symptom Diary revised to the original published version

2. Clarification of intent for urine sample analysis, minor text changes to Part A and B Time and Events tables to ensure consistency, and more comprehensive information on the allergic reaction risk

Copyright 2016 the GlaxoSmithKline group of companies. All rights reserved. Unauthorised copying or use of this information is prohibited.

## 1. PROTOCOL SYNOPSIS FOR STUDY 203820

### Rationale

In the first clinical trial of GSK2981278, once daily treatment of GSK2981278 ointment (at 0.03%, 0.1%, 0.8%, and 4%) on small test fields ( $1.13\text{ cm}^2$ ) of stable plaque(s) over 19 days appeared to be well tolerated but did not show reduction in psoriatic infiltrate thickness. It is unclear whether the apparent lack of effect on infiltrate thickness in the first-time-in-human (FTIH) study was due to the very small surface area treated, the relatively short duration of exposure, or both. Therefore the present study will evaluate the safety, tolerability, clinical effect, and systemic exposure potential of topically applied GSK2981278 ointment in subjects with plaque psoriasis by treating all plaques on the body wholly for 8 weeks. The results of this study will provide preliminary information on the safety, tolerability, and effect of the GSK2981278 ointment on plaque psoriasis at the highest safe and feasible concentration to guide subsequent development strategy.

## Objective(s)/Endpoint(s)

Part A		
Objectives	Endpoints	
Primary		

 
To evaluate the safety and tolerability of topically applied GSK2981278 in subjects with plaque psoriasis
 
To evaluate the systemic exposure of GSK2981278 following topical application in subjects with plaque psoriasis
 
	
 
Incidence and nature of adverse events (AEs) and serious adverse events (SAEs)
 
Application site tolerability assessment score
 
Change in clinical laboratory parameters, vital signs, and electrocardiogram (ECG) from baseline
 
Plasma concentrations of GSK2981278
 
	
Secondary		

 
To evaluate the clinical effect following topical application of GSK2981278 in subjects with plaque psoriasis
 
	
 
Mean percent change in Target Plaque Severity Score (TPSS) from baseline to Week 8
 
Mean percent change in Physician's Global Assessment (PGA) score from baseline to Week 8
 
Mean percent change in Psoriasis Area and Severity Index (PASI) from baseline to Week 8
 
	
Exploratory		

 
To evaluate the effect of GSK2981278 ointment on relevant gene expression
 
To investigate the delivery profile of GSK2981278 into the psoriatic skin following repeat topical applications
 
To evaluate the effect of GSK2981278 ointment on subject-reported outcomes
 
To evaluate the potential metabolites of GSK2981278 in plasma, urine, and skin from biopsies in pooled subject samples, as data allow
 
	
 
Fold change in messenger ribonucleic acid (mRNA) biomarkers from baseline to Week 8 in skin biopsy samples
 
Quantification of GSK2981278 in the skin biopsy using Matrix Assisted Laser Desorption Ionization (MALDI) imaging mass spectrometry or High-performance liquid chromatography-mass spectrometry (HPLC-MS) at Week 8
 
Mean percent change in Psoriasis Symptom Diary score from baseline to each study visit
 
Identification of any compound-derived metabolite(s) from plasma and urine and if possible estimation of relative amounts of drug related material
 
Quantification of GSK2981278-derived metabolite(s) in the skin biopsy using MALDI imaging mass spectrometry or HPLC-MS at Week 8
 
	

Part B	
Objectives	Endpoints
Primary	

 
To evaluate the safety and tolerability of topically applied GSK2981278 and its vehicle in subjects with plaque psoriasis
 
	
 
Incidence and nature of AEs and SAEs
 
Application site tolerability assessment score
 
Change in clinical laboratory parameters, vital signs, and ECG from baseline
 

 
To evaluate the clinical effect of topically applied GSK2981278 relative to vehicle control in subjects with plaque psoriasis
 
	
 
Mean percent change in TPSS from baseline to Week 8
 
Mean percent change in PGA score from baseline to Week 8
 
Mean percent change in PASI from baseline to Week 8
 

Exploratory	

 
To explore exposure-response relationship of sparse systemic exposures with the clinical endpoints (by performing population Pharmacokinetic (PK)/Pharmacodynamic (PD) analysis, if required), as data allows
 
	
 
Plasma concentrations of GSK2981278 and clinical endpoints assessed to determine the clinical effect (e.g. TPSS, PGA, and PASI)
 

 
To evaluate the effect of GSK2981278 ointment on subject-reported outcomes
 
	
 
Mean percent change in Psoriasis Symptom Diary score from baseline to each study visit
 

## Overall Design

This is a single-center, 2-part Phase I/IIa study to evaluate the safety, tolerability, clinical effect and systemic exposure potential of topically applied GSK2981278 ointment in subjects with plaque psoriasis. Drug delivery into the skin and changes in the relevant biomarkers will be explored using skin punch biopsies as well.

- Part A:** open label, single arm study
- Part B:** double-blind, randomized, 2-arm, parallel-group, vehicle-controlled study

After completion of Week 4 assessments and Week 8 assessments in Part A, the Sponsor will review the safety, tolerability, PK and clinical effect data. If data demonstrates a mean percent reduction of 40% or greater in TPSS and systemic exposure levels below the no observed adverse effect level (NOAEL) determined in the pre-clinical toxicity studies without significant safety or tolerability issues at either time point, the study will proceed to Part B.

## Treatment Arms and Duration

Each part of this study will consist of 3 periods: the screening period of up to 4 weeks, the treatment period of 8 weeks, and the follow-up period of 2 weeks. Study visits will occur at Screening; Baseline; Weeks 1, 4, and 8 during the treatment period; and Week 10 for follow-up, which will be 2 weeks after the last application of study treatment. Additional visits may occur, as needed, for early withdrawal or to follow-up on any skin

reactions or ongoing AEs. A subject's total duration of study participation will be approximately 14 weeks.

In **Part A**, subjects will receive topical application of GSK2981278 4% ointment to all affected areas of the body twice daily for 8 weeks.

In **Part B**, subjects will receive topical application of either GKS2981278 4% ointment or the vehicle ointment, according to the randomization, to all affected areas of the body twice daily for 8 weeks.

The concentration of GSK2981278 may be lowered to 2% or 0.8% in Part A and/or Part B based on the newly available safety and tolerability data.

### **Type and Number of Subjects**

In **Part A**, eight adult subjects with chronic stable plaque psoriasis will be enrolled. If subjects prematurely discontinue the study treatment, additional replacement subjects may be recruited at the discretion of the Sponsor in consultation with the investigator.

In **Part B**, approximately 18 adult subjects with chronic stable plaque psoriasis will be randomized with an allocation ratio of 2:1 to GSK2981278 4% ointment or vehicle ointment to have at least 15 evaluable subjects who comply closely with the protocol (e.g. have sufficient exposure and critical assessments completed). Subjects who were enrolled in Part A will not be eligible to participate in Part B.

If the concentration of GSK2981278 is lowered in either part of the study, additional subjects may be enrolled to have the minimum evaluable subjects in that part treated with the lower concentration of study treatment.

### **Analysis**

No formal hypothesis tests are planned. Descriptive statistics will be used to assess the key objectives of this study.

## 2. INTRODUCTION

GSK2981278 is an inverse agonist of retinoic acid receptor-related orphan receptor gamma (ROR $\gamma$ ) that is being developed for topical treatment of plaque psoriasis.

### 2.1. Study Rationale

In the first clinical trial of GSK2981278, once daily treatment of GSK2981278 ointment (at 0.03%, 0.1%, 0.8%, and 4%) on small test fields (1.13 cm^2) of stable plaque(s) over 19 days appeared to be well tolerated but did not show reduction in psoriatic infiltrate thickness. It is unclear whether the apparent lack of effect on infiltrate thickness in the FTIH study was due to the very small surface area treated, the relatively short duration of exposure, or both. Therefore the present study will evaluate the safety, tolerability, clinical effect, and systemic exposure potential of topically applied GSK2981278 ointment in subjects with plaque psoriasis by treating all plaques on the body wholly for 8 weeks. The results of this study will provide preliminary information on the safety, tolerability, and effect of the GSK2981278 ointment on plaque psoriasis at the highest safe and feasible concentration to guide subsequent development strategy.

### 2.2. Brief Background

Psoriasis is a chronic inflammatory skin disorder affecting 0.7 to 2.9% of the population in Europe and the United States [Parisi, 2013]. Plaque type psoriasis is characterized by raised, well-demarcated, erythematous oval plaques with adherent silvery scales [Nestle, 2009] and affects approximately 85 to 90% of all psoriasis patients [Griffiths, 2007]. There is substantial impairment of physical and psychological quality of life associated with the disease [DeKorte, 2004].

The primary goal of treatment for psoriasis is to improve the signs and symptoms as there is no curative treatment. Approximately 80% of psoriasis patients have mild to moderate disease, which is typically managed with topical agents. In patients with more severe disease, topical agents are often used adjunctively with either phototherapy or systemic medications. Topical corticosteroids are the mainstay of topical therapy and provide relatively high efficacy. However, local safety issues such as skin atrophy, telangiectasia, and striae distensae as well as systemic safety concerns such as hypothalamic-pituitary-adrenal (HPA) axis suppression limit their long-term use and use in sensitive areas [Menter, 2009]. Other topical agents such as vitamin D analogues and topical retinoids are available to complement the corticosteroid therapy. There is a need for an effective novel topical agent without the safety concerns associated with corticosteroids.

Although the pathophysiology of psoriasis is not fully understood, current evidence suggests that a combination of genetic, immunologic and environmental factors contributes to the disease. Growing understanding of the involvement of the immune system in the psoriasis pathophysiology indicates that Type 17 helper T-cell (Th 17) cells and their signature proinflammatory cytokine Interleukin-17 (IL-17) plays a critical role [Malakouti, 2015]. IL-17A is known to drive inflammatory pathways inherent in psoriasis pathogenesis by stimulating keratinocyte expression of multiple chemokines and increasing the expression of antimicrobial peptides and contributing to epidermal

hyperproliferation and skin barrier disruption. Increased numbers of IL-17 positive T cells and higher IL-17A messenger Ribonucleic acid (RNA) expression in psoriatic lesions compared with normal skin have been reported as well [Lynde, 2014]. In addition, the involvement of IL-17 cytokines was recently validated with monoclonal antibody (mAb) treatment. Three biologic therapies that inhibit the IL-17 cytokines have been shown to control the signs and symptoms of plaque-type psoriasis. Phase III study results have shown that a greater proportion of patients administered these agents have a higher PASI75 and PASI100 response compared to patients administered existing biologics that have different mechanisms of action (e.g., Tumor necrosis alfa (TNF- $\alpha$ ) inhibitors and T-cell inhibitors) [Langley, 2014; Sandoval, 2015; Lebwohl, 2015; Gordon, 2015].

ROR $\gamma$ t, a truncated isoform of ROR $\gamma$ , is a transcription factor involved in Th17 cell differentiation and Th17 cytokine expression. It is expressed in a few distinct types of immune cells and is described as the master regulator of Th17 cytokine expression [Ivanov, 2006].

ROR $\gamma$  is widely expressed throughout the body and has identical ligand-binding domains as ROR $\gamma$ t [He, 1998]. Compounds targeting ROR $\gamma$  are expected to modulate the activity of ROR $\gamma$ t as well. Therefore, local delivery of the selective ROR $\gamma$  inverse agonist GSK2981278 to lesional skin of psoriasis patients via topical application is expected to block the transcriptional activity of ROR $\gamma$ t leading to the local suppression of cytokine expression from skin-resident T cells and ultimately to improvement in psoriasis, with no or minimal systemic effects.

Pre-clinical data show that GSK2981278 significantly inhibits production of the Th17 signature cytokines in multiple in vitro and human tissue-based assays, including human peripheral T cells and ex vivo human skin [GlaxoSmithKline Document Number 2016N286376\_00 GSK2981278 Investigator's Brochure (IB)].

### 3. OBJECTIVE(S) AND ENDPOINT(S)

Part A	
Objectives	Endpoints
Primary	

 
To evaluate the safety and tolerability of topically applied GSK2981278 in subjects with plaque psoriasis
 
To evaluate the systemic exposure of GSK2981278 following topical application in subjects with plaque psoriasis
 
	
 
Incidence and nature of adverse events (AEs) and serious adverse events (SAEs)
 
Application site tolerability assessment score
 
Change in clinical laboratory parameters, vital signs, and electrocardiogram (ECG) from baseline
 
Plasma concentrations of GSK2981278
 

Secondary	

 
To evaluate the clinical effect following topical application of GSK2981278 in subjects with plaque psoriasis
 
	
 
Mean percent change in Target Plaque Severity Score (TPSS) from baseline to Week 8
 
Mean percent change in Physician's Global Assessment (PGA) score from baseline to Week 8
 
Mean percent change in Psoriasis Area and Severity Index (PASI) from baseline to Week 8
 

Exploratory	

 
To evaluate the effect of GSK2981278 ointment on relevant gene expression
 
To investigate the delivery profile of GSK2981278 into the psoriatic skin following repeat topical applications
 
To evaluate the effect of GSK2981278 ointment on subject-reported outcomes
 
To evaluate potential metabolites of GSK2981278 in plasma, urine, and skin from biopsies in pooled subject samples, as data allow
 
	
 
Fold change in messenger ribonucleic acid (mRNA) biomarkers from baseline to Week 8 in skin biopsy samples
 
Quantification of GSK2981278 in the skin biopsy using Matrix Assisted Laser Desorption Ionization (MALDI) imaging mass spectrometry or High-performance liquid chromatography mass spectrometry (HPLC-MS) at Week 8
 
Mean percent change in Psoriasis Symptom Diary score from baseline to each study visit
 
Identification of any compound-derived metabolite(s) from plasma and urine and if possible estimation of relative amounts of drug related material
 
Identification of GSK2981278-derived metabolite(s) in the skin biopsy using MALDI imaging mass spectrometry or HPLC-MS at Week 8
 

Part B	
Objectives	Endpoints
Primary	

 
To evaluate the safety and tolerability of topically applied GSK2981278 and its vehicle in subjects with plaque psoriasis
 
	
 
Incidence and nature of AEs and SAEs
 
Application site tolerability assessment score
 
Change in clinical laboratory parameters, vital signs, and ECG from baseline
 

 
To evaluate the clinical effect of topically applied GSK2981278 relative to vehicle control in subjects with plaque psoriasis
 
	
 
Mean percent change in TPSS from baseline to Week 8
 
Mean percent change in PGA score from baseline to Week 8
 
Mean percent change in PASI from baseline to Week 8
 

Exploratory	

 
To explore exposure-response relationship of sparse systemic exposures with the clinical endpoints (by performing population PK/PD analysis, if required), as data allows
 
	
 
Plasma concentrations of GSK2981278 and clinical endpoints assessed to determine the clinical effect (e.g. TPSS, PGA, and PASI)
 

 
To evaluate the effect of GSK2981278 ointment on subject-reported outcomes
 
	
 
Mean percent change in Psoriasis Symptom Diary score from baseline to each study visit
 

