#### **5.1. Inclusion Criteria**

A subject will be eligible for inclusion in this study only if all of the following criteria apply:

AGE
1. 18 years of age and above, at the time of signing the informed consent.
TYPE OF SUBJECT AND DIAGNOSIS INCLUDING DISEASE SEVERITY
2. Subjects with clinical diagnosis of stable plaque psoriasis for $\geq 6$ months, as confirmed by the investigator. 3. Body surface area involvement $\geq 5\%$ and $\leq 15\%$ , excluding face and intertriginous areas, at Screening and Baseline ( Appendix 2 ). The area of psoriasis involvement may include up to 2% of total BSA on the scalp with only sparse terminal hair and/or vellus hair.

4. A PGA score of <math>\geq 2</math> at Baseline (Appendix 3)
 
5. One target plaque located on the trunk or proximal parts of extremities (excluding scalp, knees, and elbows) that is at least <math>9 \text{ cm}^2</math> in size at Screening and Baseline with a Target Plaque Severity Score (TPSS) <math>\geq 5</math> and induration subscore <math>\geq 2</math>. (Appendix 4)

--

SEX
-----

6. Male

Male subjects with female partners of child bearing potential must comply with the following contraception requirements from the time of first dose of study medication until 2 weeks after the last dose of study medication.

- Vasectomy with documentation of azoospermia. The documentation on male sterility can come from the site personnel's: review of subject's medical records, medical examination and/or semen analysis, or medical history interview.

- Male condom

The allowed method of contraception is only effective when used consistently, correctly and in accordance with the product label. The investigator is responsible for ensuring that subjects understand how to properly use these methods of contraception.

7. Female of non-reproductive potential (FNRP)

A FNRP is eligible to participate in this study if she meets at least one of the following conditions:

- Females with one of the following procedures documented and no plans to utilize assisted reproductive techniques (e.g., in vitro fertilization or donor embryo transfer):

- Bilateral tubal ligation or salpingectomy
- Hysteroscopic tubal occlusion procedure with follow-up confirmation of bilateral tubal occlusion
- Hysterectomy
- Bilateral Oophorectomy (surgical menopause)

- Post-menopausal women (including all women over 60 years of age, see below),

Post-Menopause criteria

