## DIAGNOSTIC ASSESSMENTS AND OTHER CRITERIA

12. Presence of hepatitis B surface antigen (HBsAg), positive hepatitis C antibody test result at screening or within 3 months prior to first dose of study treatment.

13. A positive pre-study drug/alcohol screen.

14. A positive test for human immunodeficiency virus (HIV) antibody.

15. **For Part B only**-the subject has participated in Part A of this study.

16. The subject has participated in a clinical trial and has received an investigational product within the following time period prior to the first dosing day in the current study: 4 weeks, 5 half-lives or twice the duration of the biological effect of the investigational product (whichever is longer).

17. Prolonged exposure to natural or artificial sources of ultraviolet (UV) radiation (e.g., exposure to sunlight other than that associated with usual daily activities, use of tanning booth, etc.) within 2 weeks prior to the Day 1 visit or intention to have such exposure during the study, thought by the investigator likely to modify the subject's psoriasis.

18. In the opinion of the investigator or physician performing the initial examination the subject should not participate in the clinical trial, e.g. due to probable noncompliance, inability to understand the trial and give adequately informed consent, or inability to complete the Psoriasis Symptom Diary ([Appendix 5](#)).

19. Close affiliation with the investigator (e.g. a close relative) or persons working at bioskin GmbH or subject is an employee of sponsor.

20. Subject is institutionalized because of legal or regulatory order.

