### **7.9. Value Evidence and Outcomes**

#### **7.9.1. Psoriasis Symptom Diary**

The Psoriasis Symptom Diary was developed to assess daily self-reports of psoriasis symptoms and the functional impact related to the underlying pathophysiology of the disease [Strober, 2013]. Questions about how severe and how bothersome various signs and symptoms are to the subject are answered using an 11-point numerical rating scale ([Appendix 5](#)). In this study, subjects will be asked to complete the Psoriasis Symptom Diary questionnaire at the clinic during the scheduled visits.

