### 9.2. Sample Size Considerations

#### 9.2.1. Sample Size Assumptions

Sample size is based on feasibility and the estimated number of subjects expected to provide reasonable information on the key objectives of the study.

For Part A:

Summary statistics, such as mean % of reduction in TPSS, mean % reduction in PGA and mean % of reduction in PASI will be estimated. With 8 evaluable subjects, precisions on these estimates are assessed as below.

Endpoint	Assumptions	Sample Size	95%CI estimate
Mean % reduction in TPSS	50% reduction with 20% standard deviation will be observed	N=8	33.3% - 66.7%
Mean % reduction in PGA	50% reduction with 30% standard deviation will be observed	N=8	24.9%-75.1%
Mean % reduction in PASI	50% reduction with 25% standard deviation will be observed	N=8	29.1% -70.9%

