#### 12.8.4. Recording of AEs and SAEs

##### AEs and SAE Recording:

- When an AE/SAE occurs, it is the responsibility of the investigator to review all documentation (e.g., hospital progress notes, laboratory, and diagnostics reports) relative to the event.
- The investigator will then record all relevant information regarding an AE/SAE in the CRF
- It is **not** acceptable for the investigator to send photocopies of the subject's medical records to GSK in lieu of completion of the GSK, AE/SAE CRF page.
- There may be instances when copies of medical records for certain cases are requested by GSK. In this instance, all subject identifiers, with the exception of the subject number, will be blinded on the copies of the medical records prior to submission of to GSK.
- The investigator will attempt to establish a diagnosis of the event based on signs, symptoms, and/or other clinical information. In such cases, the diagnosis will be documented as the AE/SAE and not the individual signs/symptoms.
- Subject-completed Value Evidence and Outcomes questionnaires and the collection of AE data are independent components of the study.
- Responses to each question in the Value Evidence and Outcomes questionnaire will be treated in accordance with standard scoring and statistical procedures detailed by the scale's developer.
- The use of a single question from a multidimensional health survey to designate a cause-effect relationship to an AE is inappropriate

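### The exploratory Psoriasis Symptom Diary endpoint is fixed as a mean percent change with no minimum diary score at entry, so it is undefined at a zero baseline and unstable at a low one; absolute change would serve better

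*Protocol*

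**What the plan says.** Protocol Section 3 lists the diary endpoint, for Part A and again for Part B, as "Mean percent change in Psoriasis Symptom Diary score from baseline to each study visit". The synopsis uses the same wording. It is exploratory in both parts.

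Section 7.9.1 says that the diary questions "are answered using an 11-point numerical rating scale" and that subjects fill in the diary at clinic visits. The instrument (Appendix 5) was removed for copyright. On scoring, Section 12.8.4 says that questionnaire responses "will be treated in accordance with standard scoring and statistical procedures detailed by the scale's developer".

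Section 5.1 requires a PGA of at least 2, and a target plaque with a TPSS of at least 5 and induration of at least 2. For the diary, the only entry condition is in Section 5.2, criterion 18, which gives "inability to complete the Psoriasis Symptom Diary" as an example of a reason for exclusion. No minimum diary score is set.

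Sections 9.4.1 and 9.4.2 allow an absolute-change summary for PASI. Section 9.4 names no diary summary, so the endpoint wording is the only diary measure that the protocol states.

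**The concern.** A percent change needs a denominator that is not zero and preferably not small. The entry criteria secure this for TPSS and PGA but not for the diary.

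Two things follow. A subject who scores 0 at baseline has no percent change. If such subjects are left out, the omission is one-sided, because a subject at 0 can only stay the same or worsen. A subject with a low score has the opposite effect: improvement cannot exceed 100%, while worsening can be several hundred percent, so one such subject can pull the group mean towards worsening.

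With 8 subjects in Part A and a planning figure of 5 evaluable vehicle subjects in Part B, there is little to average this out. What is at stake is how the only subject-reported result reads.

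**Working it through.** **Inputs from the protocol.** Part A has 8 evaluable subjects; Part B has 10 active and 5 vehicle (Section 9.2.1). The TPSS entry floor is 5 (Section 5.1) and its maximum is 12 (Section 7.4.1). Diary items have 11 points (Section 7.9.1). The published diary has 16 questions (Appendix 11, which records the return to that version).

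**Assumptions.** Items run from 0 to 10. The baseline distribution is unknown, so zero rates are shown over a range. All subject scores below are invented to show how the measure behaves; they are not forecasts.

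The plan gives no precision or power for the diary, so there is no diary figure to reproduce.

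**1. Definition.** Percent change = 100 × (visit − baseline) / baseline. It is undefined when baseline = 0.

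**2. Largest possible worsening.**
- TPSS at its entry floor: 100 × (12 − 5)/5 = +140%.
- Diary item from 1: 100 × (10 − 1)/1 = +900%.

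**3. One low baseline among 8 subjects.** Seven subjects go from 8 to 4 (−50%, −4 points each). The eighth varies:

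| Eighth subject | Mean percent change | Mean change in points |
|---|---|---|
| 1 to 3 (+200%) | (7 × −50 + 200)/8 = −18.75% | (7 × −4 + 2)/8 = −3.25 |
| 1 to 5 (+400%) | (7 × −50 + 400)/8 = +6.25% | (7 × −4 + 4)/8 = −3.0 |
| 0 to any score, left out | (7 × −50)/7 = −50% | still defined for all 8 |

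The first row is distortion; the second is reversal. With the other seven at −50%, reversal needs the eighth above 7 × 50 = +350%. On a 0–10 item that is possible only from a baseline of 1 or 2, since 3 to 10 is +233%.

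**4. One low baseline among 5 subjects.** Four go from 5 to 4 (−20% each) and one goes from 1 to 3 (+200%). Mean percent change = (4 × −20 + 200)/5 = +24%. Mean change = (4 × −1 + 2)/5 = −0.4 points.

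**5. How often a zero baseline would occur.** If a score is 0 at baseline with probability p, independently across subjects, the chance of at least one among n is 1 − (1 − p)^n:

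| p | n = 8 | n = 15 |
|---|---|---|
| 1% | 8% | 14% |
| 5% | 34% | 54% |
| 10% | 57% | 79% |
| 20% | 83% | 97% |

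**6. Item or total.** A zero total needs all 16 items at 0. If each item were 0 half the time, independently, the probability would be 0.5^16 ≈ 0.000015 per subject. Items are likely to be positively correlated, which raises this figure, but the subjects have active disease by Section 5.1. Step 5 is therefore a concern for items and hardly one for a total.

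Instability does not depend on the level. Multiplying the scores in step 3 by ten (80 to 40, and 10 to 30) gives the same −18.75%, against a mean change of −32.5 points. Low totals are simply less likely than low item scores.

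**The case against.** The strongest reply is that much of this depends on text that cannot be seen. The endpoint speaks of a diary score, Appendix 5 is removed, and scoring is delegated to the developer. A reader might infer that the protocol fails to define a total score; the documents do not support that. If a total is used, undefined values all but disappear. This stands, and it narrows the zero-baseline part to item-level analysis.

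A second reply is that zero-baseline handling and the scoring level belong in the analysis plan, to which Section 9 refers for detail. This also stands: their absence is no fault, and nothing in the protocol says that zero-baseline subjects will be dropped. But the choice of percent change is made in the protocol itself. Section 9.4.3 leaves room to add absolute change, yet the stated endpoint would remain percent change.

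A third reply is that percent change matches the TPSS, PGA and PASI endpoints. That is a real convenience, and a reason to keep it as a supplement.

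A reader might also infer that burning or pain caused by the ointment would go unseen. The documents do not support this. Application site tolerability and adverse events are primary endpoints with their own assessments, Section 12.8.4 treats questionnaires and adverse event collection as independent, and no visible text shows that the diary asks about burning or pain.

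**Conclusion.** The point holds, and it is minor. The protocol commits the diary endpoint in both parts to a measure that has no value at a baseline of 0 and behaves poorly near it, without the entry floor that protects TPSS and PGA. In groups of 8 or 5, one low baseline can distort the mean or change its sign: +6.25% against −3.0 points, and +24% against −0.4 points, in the constructed examples.

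This rests on a 0–10 item range and on some subjects having low scores at baseline. A reader might conclude that low baselines will dominate the result; without a baseline distribution the documents show only that they can.

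Little depends on the outcome. The endpoint is exploratory, no formal hypothesis tests are planned (Section 9.1), no sample size rests on it, and the criteria for proceeding to Part B use TPSS, systemic exposure, and safety and tolerability (Section 4.1).

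**What to change.** In the synopsis and Section 3, for both parts, define the diary endpoint as mean absolute change from baseline in the diary score at each study visit, using items or a total as the developer's scoring defines. Keep mean percent change as a supplementary summary for subjects with a non-zero baseline, and report how many subjects that leaves.

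Absolute change is defined at a baseline of 0 and bounded by the scale. No new data are needed. The cost is a minor wording amendment, with the ethics committee review that Section 10.2 requires for amendments as applicable, and a diary summary less directly comparable with the percent-change summaries of TPSS, PGA and PASI.
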